The Principal Investigator will refine existing protocols for assuring data accuracy and protocol compliance. Such protocols will include data verification and protocol compliance checks as well as other quality assurance procedures. The Principal Investigator will also be responsible for ensuring that the data for the project are securely stored, that storage is in compliance with University and federal regulations and that no unauthorized persons have access (electronic or physical) to any participant-identifiable data.

STATISTICAL CONSIDERATIONS

In this section, we outline general strategies for analysis of startle potentiation, EMA, and treatment outcome that are used to address our four aims. We sketch out clear exemplars of analysis options for this rich dataset. Of course, there are numerous supplemental analyses that space constraints prevent describing here.

ANALYSIS OF STARTLE POTENTIAION (AIM 1). The analysis of startle potentiation for Aims 1 & 1.1 across experimental tasks can be accomplished within very similar General Linear Models (GLMs). In each analysis, startle potentiation will be analyzed in a GLM with Threat Uncertainty (low vs. high probability for Threat Probability task; fixed vs. variable duration for Threat Duration task) as the focal within-subject factor.

Analysis of Aim 1.1 will use the full sample as a focal between-subject factor. Support for the stress neuroadaptation thesis following chronic tobacco use would be offered by a Smoking Group X Threat Uncertainty interaction with selectively greater startle potentiation among smokers in uncertain threat for each task. Analysis of Aim 1.2 will use both pre-quit sessions and include Deprivation Status (nicotine deprived vs. non-deprived) as a focal within subject factor. Support for the stress neuroadaptation thesis when nicotine deprived would be offered by a Deprivation Status X Threat Uncertainty interaction with selectively greater startle potentiation among deprived smokers in uncertain threat for each task.

Additional covariates will be considered for each GLM to reduce error variance and increase power (e.g., resting startle response, task order, block order). All experiments include equal numbers of men and women to allow for preliminary examination of possible sex effects. Trait individual difference variables (e.g., individual differences in anxiety, depression, levels of tobacco dependence; see section C2.2) can be included in the GLMs to provide exploratory tests for potentially interesting moderators. Quantitatively measured withdrawal symptoms (WSWS) and smoking urge (QSU) can be included in supplemental analysis to clearly link deprivation status effects on startle potentiation to these proximal processes. Given that all participants complete both threat tasks, follow-up GLMs can include task as a within-subject factor to determine if effects are consistent across tasks that involve different manipulations of anxiety (i.e., low probability vs. temporally uncertain threat). This will provide important construct validation and potential conceptual replication of possible anxiety findings.

Analysis of Ecological Momentary Assessments of Stressors, Affect, Urge and Smoking (AIMS 2, and 4.3)

Analysis of EMA data will follow directly from procedures described by our Co-I, [name], in McCarthy, Piasecki, Fiore, & [name] (2006). Although the focal questions in McCarthy et al (2006) were different, the nature of that dataset was very similar in that it included multiple weeks of 4X daily EMA reports of stressors,

affect, cigarette use, and withdrawal symptoms. The within-subjects, repeated measures design associated with EMA survey make it suitable for **growth-curve modeling**, a technique that estimates change over time via **multilevel modeling** (147,148). Although time is not a focal factor in our analysis, growth curve modeling is well-suited for these data and our questions because it can easily accommodate missing data and unequal intervals between assessments that result from pseudo-randomly selecting assessment times during each day. This multilevel model allows us to predict “occasion-level” (level 1) responding associated with affective response, urge, or smoking with other occasion-level variables (e.g., stressor occurrence), or “person-level” (level 2) variables (e.g., startle potentiation measures from cued threat task). Therefore, these models will provide clear and powerful tests to determine if laboratory startle potentiation “biomarkers” of stress neuroadaptations predict individual differences in overall levels of negative affect, urge, or smoking over the 3-weeks of EMA controlling for stressor exposure (AIM 2.1). Furthermore, these same models will provide tests if startle potentiation measures of stress neuroadaptation predicts individual differences in the size of the occasion-level stressor effects on negative affect, urge and smoking (i.e., stress-induced negative affect, urge, and smoking). In other words, do our laboratory stress neuroadaptation measures predict stressor-affect, stressor-urge, and stressor-smoking covariation or coupling over time (AIM 2.2). Treatment condition can be included as a moderating between-subject factor to test if the relationship between startle potentiation and overall levels and coupling of EMA measured affect, urge and smoking differ generally when withdrawal symptoms are treated via combo NRT (AIM 4.3). As with GLM analyses, these multilevel models can accommodate other exploratory person-level moderators of these effects (e.g., trait anxiety, depression, level of dependence, sex). As before, the models can also include task as a factor to determine if anxiety as measured in the laboratory task displays comparable relationships with occasion-level EMA data

Analysis of Treatment Outcome (AIMS 3, 4.1, 4.2): Number of cigarettes smoked (17,18), point prevalence abstinence and continuous abstinence (as defined by the SRNT Workgroup on Biochemical Confirmation (149)) will be analyzed in Generalized Linear Models with time (1 week vs. 2 weeks) as a within subject factor. Startle potentiation measures from the cued threat task will be included as quantitative regressors to test if our laboratory stress neuroadaptation biomarkers predict treatment outcome measures (Aim 3). As above, treatment condition can be included as a moderating between subject factor to test if the relationships between startle potentiation and treatment outcome differ generally when withdrawal symptoms. Finally, mediation analyses can be conducted to determine if NRT alters startle potentiation measures at one-week post quit (AIM 4.1) and the startle potentiation measures mediate NRT effects on smoking outcome measures (AIM 4.2).

C4.3: Sample Size Justification. The primary analyses of startle potentiation will be accomplished within the General Linear Model (GLM). The analyses of smokers test for a two way interaction between Deprivation Status and Threat Uncertainty. Cohen (150) defines 0.15 for the squared multiple partial correlation as a medium effect size for GLM analyses. To be conservative, we powered our experiments to provide 90% power to detect a somewhat smaller (0.10) effect size. N=142 will provide 90% power to detect a squared multiple partial correlation of 0.10 for the interaction in a model that contains the two main effects and interaction based on formula provided by Cohen. We then increased this sample size to the round 150 within each Treatment Group to provide flexibility to counterbalance all relevant additional task factors. This yields N=300 across the two Treatment Groups. Given that the multilevel models that will be used to test questions about the EMA data are essentially GLMs fit at two separate levels of analysis (occasion and person levels), N=150 within each Treatment Group will provide comparable high power to test person-level predictors of both occasion-level intercepts (e.g., overall smoking, levels of negative affect) and stressor coefficients (e.g., stress-instigated smoking or negative affect).

DATA AND RECORD KEEPING

All data will be obtained directly from research participants. No access to medical records or other sources of information is required. Data include participants' self reports on questionnaires, via text messages (see section on EMA) and physiology in the laboratory. All data are digitally stored with ID number only. Data are managed by the PI. Consent forms are separated from other data and stored in a locked room in a locked file cabinet.

We will register this study at the Open Science Framework (osf.io). The Open Science Framework (OSF) is a free, open source web application that connects and supports the research workflow, enabling scientists to increase the efficiency and effectiveness of their research. Researchers use the OSF to collaborate, document, archive, share, and register research projects, materials, and data. OSF is used as a data repository for sharing de-identified study data from published analyses with other researchers as recommended by NIH. OSF is also a recommended data management site per UW Research Data Services (<http://researchdata.wisc.edu/>).

We will make de-identified processed data, study materials (e.g., questionnaires), and data analysis code from this study publicly available to share with the research community. We plan to share these data in online repositories on the Open Science Foundation (OSF: <https://osf.io/ukhcf/>). Specifically, the data that we will share include physiological measures (e.g., EMG startle response) and self-report surveys/questionnaires. All participants' data will be de-identified.

REFERENCES CITED

1. Bolt DM, [name] ME, Theobald WE, [name] TB. Why two smoking cessation agents work better than one: Role of craving suppression. *Journal of Consulting and Clinical Psychology* [Internet]. 2011 Nov 21 [cited 2011 Dec 5];Available from: <http://www.ncbi.nlm.nih.gov/pubmed/22103958>
2. Japuntich SJ, [name] ME, Leventhal AM, Bolt DM, [name] TB. The effect of five smoking cessation pharmacotherapies on smoking cessation milestones. *J Consult Clin Psychol*. 2011 Feb;79(1):34–42.
3. Smith SS, [name] ME, Bolt DM, Fiore MC, Wetter DW, Cinciripini PM, et al. Development of the Brief Wisconsin Inventory of Smoking Dependence Motives. *Nicotine Tob. Res.* 2010 May;12(5):489–99.
4. Bolt DM, [name] ME, McCarthy DE, Japuntich SJ, Fiore MC, Smith SS, et al. The Wisconsin Predicting Patients' Relapse questionnaire. *Nicotine Tob. Res.* 2009 May;11(5):481–92.

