In summary, following smokers during the first two weeks of a smoking cessation attempt provides important laboratory-to-clinical translational benefits. The use of a two week surrogate endpoint for measuring cessation outcomes is innovative and also resource efficient. The use of EMA to track smoking as well as stressor-smoking, stressor-affect and stressor-urge relationships is also innovative in the combination with laboratory measures. These data will allow us to directly examine if 1) our laboratory measures of negative affective response to stressors predict individual differences in stressor coupling with negative affect, urge, and smoking (AIM 2), 2) our laboratory measures predict smoking cessation outcomes across all smokers, regardless of medication group (AIM 3), 3) our laboratory measures differentially predict smoking cessation outcomes across combo NRT vs. placebo as would be expected if combo NRT reduces the influence of negative affect on smoking (AIM 4). To further evaluate AIM 4, we will also re-administer our laboratory cued threat task at 2 weeks post-quit to determine if combo NRT alters negative affective response to stressors and to test if this laboratory measure obtained during treatment mediates combo NRT effects (relative to placebo NRT with counseling) on smoking cessation outcome.

SPECIFIC AIMS

Neuroscience research with animal models implicates neuroadaptation in the stress response as a critical mechanism in the etiology of addiction across multiple classes of drugs including nicotine (22–24). Repeated homeostatic adjustments in the brain's stress systems due to chronic drug administration eventually lead to persistent compensatory adaptations in the structures involved in emotional response and its regulation. Among smokers, these stress neuroadaptations result in dysregulated negative affect when nicotine-deprived and provide the strong motivational press for further smoking that manifests as urge and increased risk for relapse (21,25).

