1.1: Nicotine deprived smokers will display selectively increased negative affect measured via startle potentiation during uncertain (vs. certain) threat relative to non-deprived smokers.

AIM 2: Examine the impact of stress neuroadaptation on negative affect, smoking urge, and smoking in response to stressors. Laboratory startle potentiation measures of stress neuroadaptation will predict ecological momentary assessment measures of:

2.1 ...overall levels of negative affect and urge
2.2 ...within-smoker covariation (i.e., coupling) of episodic stressors with negative affect, urge, and smoking (i.e., stressor-induced negative affect, urge and smoking).

AIM 3: Examine the impact of this stress neuroadaptation on smoking during the first two weeks of smoking cessation.

3.1: Laboratory startle potentiation measures of stress neuroadaptation will predict overall smoking during the first two weeks post-quit as well as measures of point prevalence abstinence and continuous abstinence measured at 2 weeks post-quit.

AIM 4: Determine if treatment of withdrawal via NRT reduces the influence of stress neuroadaptation.

4.1: Combo NRT with counseling (vs. placebo NRT with counseling) will reduce startle potentiation measures obtained at one week post-quit.

4.2: The effect of combo NRT (vs. placebo NRT with counseling) on smoking and related outcome measures will be mediated by change in startle potentiation measures from pre-quit to post-quit.

4.3: Treatment of withdrawal symptoms via combo NRT will attenuate the predictive strength of pre-quit startle potentiation measures with respect to overall levels of negative affect, urge, and smoking and stressor-induced negative affect, urge, and smoking.

RESEARCH DESIGN AND METHODS

C1: BRIEF OVERVIEW

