C2.4.1: Design Considerations and Justification: We discussed our careful considerations regarding our focus on the Cessation period and the use of this surrogate endpoint during a smoking cessation attempt in section A5 earlier. We also carefully considered an alternative design where we measured negative affective response during a single session of NRT administration to deprived smokers in the laboratory rather than at one week into a quit attempt. Although this alternative would be simpler, it may fail to capture a number of critical elements that are relevant to real-world quit attempts. In particular, the affective experience is likely quite different during a temporary deprivation period vs. a similar duration of deprivation in the context of an intended permanent cessation of use. Furthermore, the effects of deprivation likely vary over time during the cessation attempt as regulatory resources become drained and homeostatic adaptation processes are recruited (104,129–131). Our current design indexes negative affect both early in deprivation (during the pre-quit deprived session) and after one week of cessation. In addition, the 2 week quit period provides the opportunity for detailed real world measurement of stressor-affect, stressor-urge, and stressor-smoking relations via EMA (see below) that would not be available with the single NRT administration in the laboratory. We believe these benefits justify our current design.

Participants are instructed to continue NRT even if they fail to maintain complete abstinence during their quit attempt. There is evidence that participants benefit from reduced smoking on NRT even if full abstinence is not obtained or maintained (20). This procedure will allow all participants to be included in analyses of EMA cessation measures. Furthermore, analyses of the cued threat task that is administered at one week post-quit can retain all participants but include regressors/covariates to model the amount of smoking (and medication use) during the first week.

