During this visit, smokers will complete their second administration of the two NPU Task that was completed at their previous visit session. This assessment during combo NRT (or placebo) use will allow for tests of the effects of medication on our laboratory measures of negative affective response to uncertain threats. Furthermore, by measuring negative affective response to threats during medication use, we can now test if response on these tasks during medication use mediates smoking cessation outcomes associated with treatment of withdrawal symptoms via combo NRT.

C2.6.1: Design Considerations and Justification. We considered measuring cessation outcomes at later time points. However, the resources necessary to measure cigarette use after the EMA period has ended and/or to obtain biological confirmation of smoking status at later points was considered too large. As noted earlier, our primary focus is on the Cessation phase during the first 2 weeks. We expect the negative affective processes that are the focus of this application to have their greatest influence on cessation success during the first two weeks post-quit when withdrawal symptoms are most robust. Furthermore, smoking at later time points is expected to be increasing influenced by factors outside the focus of this application and therefore will display reduced relationships with our laboratory measures of negative affect. In addition, as the proportion of the sample that has relapsed increases with time since quit, power will be diminished to test our aims. For these reasons, we have focused our resources on this two week cessation period.

C3: EXPERIMENTAL CUED THREAT TASK

Building on basic affective neuroscience research with humans and animals reviewed earlier (30,31,62,75), we have developed and validated a laboratory task that is designed to measure negative affective response to threats broadly as well as selectively parse fear and anxiety. Consistent with current conceptualizations of fear and anxiety, the task presents participants with threats that are either certain or uncertain to assess their fear and anxiety, respectively. We manipulate uncertainty in the temporal domain by including conditions of imminent threat (shocks administered 5s post cue onset; certain threat) vs. distal/temporally uncertain threat (shocks administered anywhere post cue onset or during ITIs; uncertain threat). As per standard procedures in

[figure not shown]

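### Aim 4.2 defines the startle mediator in two ways and plans no adjustment for first-session startle, so the NRT mediated effect can be understated, overstated or wrong-signed, depending on values the plan does not give

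*Combined protocol and SAP*

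**What the plan says.** Four places describe the mediator for Aim 4.2, and they do not agree.

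- SPECIFIC AIMS, Aim 4.2: the NRT effect on smoking "will be mediated by change in startle potentiation measures from pre-quit to post-quit". This is a change score.
- A5, closing summary: the task is repeated post-quit "to test if this laboratory measure obtained during treatment mediates combo NRT effects". This is the post-quit level.
- C2.6: "we can now test if response on these tasks during medication use mediates smoking cessation outcomes". This is again the post-quit level.
- Analysis of Treatment Outcome (AIMS 3, 4.1, 4.2): the one sentence on mediation says that analyses are possible to see whether "the startle potentiation measures mediate NRT effects on smoking outcome measures (AIM 4.2"). It does not say whether this means the level or the change, and it gives no equations.

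First-session startle potentiation is not named as a covariate for this aim anywhere. The covariates that are named serve other analyses. For the Aim 1 models: "Additional covariates will be considered for each GLM to reduce error variance and increase power (e.g., resting startle response, task order, block order"). For the post-quit task, C2.4.1 allows analyses to "include regressors/covariates to model the amount of smoking (and medication use) during the first week". Separately, Aim 3.1 predicts that "Laboratory startle potentiation measures of stress neuroadaptation will predict overall smoking during the first two weeks post-quit".

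**The concern.** Startle is measured at a first session (X) and again after quitting (M). Using M − X as the mediator without X elsewhere in the model forces the two measurements into the smoking equation with equal and opposite slopes. If smokers who are more reactive at the first session also smoke more after quitting, over and above their post-quit startle, that constraint is wrong and pulls the mediator's slope towards zero or past it. Using M alone has the opposite fault, because any stable reactivity that M shares with X is credited to the mediator.

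Aim 4.2 is the test of whether NRT works by reducing reactivity to uncertain threat. Depending on the definition chosen at analysis, the same data could show no mediation, exaggerated mediation or mediation in the wrong direction. Nothing in the plan fixes that choice in advance.

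**Working it through.** **No plan figure to reproduce.** The sample size section gives N = 142, raised to 150 per treatment group and 300 in all, for the deprivation-by-uncertainty interaction. It states no effect size or power for mediation.

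**Inputs from the documents.** There are two randomised arms of 150 (C1, C4.3). Study medication is handed out after the task (C2.3), so X precedes medication and is independent of arm by design.

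**Inputs assumed.** All slopes, SDs, the between-session correlation rho and the NRT effect on startle (a).

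**Change score without X.** Take Y = bM + gX + arm term + error, and D = M − X, with within-arm SDs s1 (first session) and s2 (post-quit). The slope of Y on D given arm is

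[b(s2² − rho·s1·s2) + g(rho·s1·s2 − s1²)] / (s1² + s2² − 2·rho·s1·s2).

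With s1 = s2 = 1 this is [b(1 − rho) − g(1 − rho)] / [2(1 − rho)] = (b − g)/2, whatever rho is. Because X is independent of arm, the NRT effect on D is still a, so the fraction of the mediated effect recovered is (1 − g/b)/2:

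| g/b | fraction recovered |
|---|---|
| −1 | 1.00 |
| −0.5 | 0.75 |
| 0 | 0.50 |
| 0.5 | 0.25 |
| 1 | 0.00 |

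**Unequal SDs, rho = 0.5.**
- s2/s1 = 1.25, g = 0: (1.5625 − 0.625)/(1 + 1.5625 − 1.25) = 0.9375/1.3125 = 0.71. At g = b it is (0.9375 − 0.375)/1.3125 = 0.43.
- s2/s1 = 0.8, g = 0: (0.64 − 0.40)/(1 + 0.64 − 0.80) = 0.24/0.84 = 0.29. At g = b it is (0.24 − 0.60)/0.84 = −0.43.

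**Post-quit startle without X.** With equal SDs the slope is b + rho·g, so the fraction is 1 + rho·g/b. At rho = 0.6 this is 1.00 for g = 0, 1.30 for g = b/2 and 1.60 for g = b.

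**X in both equations.** Since bM + gX = b(M − X) + (b + g)X, the change score and the post-quit level then have the same slope b, and the mediated effect a·b is recovered.

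**Simulation.** Settings: N = 300, a = −0.33 SD, equal SDs, rho = 0.5 unless stated, a continuous smoking outcome, and mediation declared when both paths are significant at two-sided 5%. With b = 0.2 the true mediated effect is −0.33 × 0.2 = −0.066.

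| b, g | change score, no X | post-quit only | X in both equations |
|---|---|---|---|
| 0.2, 0 | 36% | 77% | 77% |
| 0.2, 0.1 | 10% (mean −0.016) | – | 75% (mean −0.065) |
| 0.2, 0.2 | 4% | – | 76% |
| 0, 0.2 (no mediation) | 32%, wrong sign | 33% | 4% |
| 0.2, 0, rho = 0.7 | – | 76% | 68% |

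The first three rows and the last are power. The fourth is the false-positive rate. A dash marks a cell not reported here.

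**The case against.** The strongest reply is that the plan is silent rather than wrong. The mediation text is one permissive sentence in a section that presents itself as a sketch of options, and nothing excludes first-session startle. The same section says "Startle potentiation measures from the cued threat task will be included as quantitative regressors", without naming the session. If first-session startle were among those regressors in the mediation outcome model, the distortion of the smoking slope would disappear. This stands: the omission is an absence of specification, not a stated choice.

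A reader might infer that the change score recovers at best half of the effect. The documents do not support that, because it needs equal SDs and g ≥ 0. With g = −0.05 and b = 0.2 the fraction is (0.2 + 0.05)/(2 × 0.2) = 0.63. If change itself drives smoking (g = −b), which is one way to read Aim 4.2, the change score is unbiased.

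A reader might also infer that Aim 3.1 makes both definitions wrong. It does not. Aim 3.1 concerns prediction and mentions no adjustment for post-quit startle. With equal SDs its slope within arm is g + rho·b, which is positive even at g = 0. In that case post-quit startle alone is unbiased and, at high rho, somewhat more powerful than the adjusted analysis.

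Finally, the planned outcomes are cigarette counts and two abstinence measures in Generalized Linear Models, so the simulated percentages do not carry over exactly.

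**Conclusion.** The point holds as one of definition and specification. The aims name a change score, two other sections name the on-treatment response, and no section plans adjustment for first-session startle. The two unadjusted analyses can give materially different answers.

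The formulas are exact for a linear outcome model with equal SDs. How large the error would be in this trial cannot be known from the documents: b, g, rho, the SDs and the NRT effect on startle are all assumptions here. Aim 3.1 makes g > 0 plausible without implying it. It would therefore go too far to say that the planned analysis will hide mediation. What can be said is that the result depends on an unstated choice, and that adjusting for first-session startle removes that dependence.

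The adjustment does not settle a separate problem. The post-quit task at the 2-week visit comes after the two weeks of smoking it is meant to mediate, so recovering a·b in these calculations does not establish the causal order.

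**What to change.** Name one mediator, post-quit startle potentiation, in A5, Aim 4.2, C2.6 and the treatment-outcome analysis section. In both the mediator model (post-quit startle on arm) and the outcome model (smoking on post-quit startle and arm), enter two covariates: the same startle potentiation score from the first session, and deprivation status at that session. Deprivation status is needed because C2.2 and C2.3 place deprived smokers' first session the day after quitting starts and non-deprived smokers' session before it.

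Both covariates are already collected. The cost is a sentence in each place and two degrees of freedom per model. If g = 0 and rho is high there is also a modest loss of power against post-quit startle alone: about 68% against 76% at rho = 0.7 under the assumed effects.

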All participants report some demographic information, their current affective state (Positive and Negative Affect Scales-PANAS (120), provide information on a broad-band personality measure (Brief Multidimensional Personality Questionnaire- bMPQ); (121) and supplemental measures of trait affectivity relevant to individual differences in anxiety including the Intolerance of Uncertainty Inventory, (122), and the Anxiety Sensitivity Inventory (123). Individual differences in depressive symptoms will also be recorded Center for Epidemiologic Studies Depression Scale Revised (CESD-R; 125) and the Depression Anxiety Stress Scale-21 (DASS-21).

These measures are available to serve as covariates to increase power to test for focal effects on relevant outcome measures. They are also available as possible individual difference moderators in supplemental analyses. After completing the self-report measures, participants schedule their first experimental session. Participants are randomized to either a nicotine deprived or non-deprived condition and instructed to abstain from all nicotine containing products for 24 hours prior to their nicotine deprived session or to continue their normal pattern of smoking prior to their non-deprived session.

Finally, participants receive brief cessation counselling, schedule their experimental visits and quit date, and are provided with verbal and written instructions about the 3-week daily EMA survey that begins one week before their quit date.

C2.3: Laboratory Experimental Session(s)

All participants complete the cued threat task (NPU; see section C3 below) in each of two separate experimental sessions. Their first session is either nicotine deprived and non-deprived in a counterbalanced order, the final is 2 weeks post-quit. The deprived group completes their first experimental session the day after the start of their quit attempt, and the non-deprived group completes it before the start of their quit attempt. Data across the two experimental sessions will be used to provide sensitive within-subjects tests of deprivation effects on startle potentiation measures of stress neuroadaptation (Aim 1) and to address all subsequent Aims (2-4).

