our and other laboratories, shock intensity during these tasks is calibrated to each participant's individual sensitivity threshold, which is assessed prior to the main task during each experimental session to reduce individual differences (34,62,64,135). Startle potentiation is the primary dependent measure of affective response. As reviewed earlier, basic affective neuroscience research has indicated that startle potentiation is a sensitive and selective index of the neurobiological substrates of fear and anxiety, respectively, during conditions of certain vs. uncertain threat (30,72,74).

Participants in the non-deprived group will complete the task once pre-quit; in the deprived group, immediately post-quit, while both groups will also complete the task 2 weeks post-quit (counterbalanced) in separate experimental sessions separated by approximately two weeks. Task details are provided below. Task order within an experimental session is counterbalanced across all participants. We have preliminary data among 23 smokers in the context of an ongoing study that verify that smokers will tolerate multiple administrations across separate days of similar cued threat tasks.

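### At session 1, nicotine deprivation and having started to quit coincide completely, so Aim 1 estimates their combined effect and not that of deprivation alone

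*Combined protocol and SAP*

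**What the plan says.** **Schedule.** Section C2.2: "Participants are randomized to either a nicotine deprived or non-deprived condition". Section C2.3: "The deprived group completes their first experimental session the day after the start of their quit attempt", whereas "the non-deprived group completes it before the start of their quit attempt". Section C3 repeats this: "Participants in the non-deprived group will complete the task once pre-quit; in the deprived group, immediately post-quit". Each person has one further session, and C2.3 says that "the final is 2 weeks post-quit". C2.3 also puts counseling and study medication after the task at session 1.

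**Interpretation.** Specific Aim 1.1: "Nicotine deprived smokers will display selectively increased negative affect measured via startle potentiation during uncertain (vs. certain) threat relative to non-deprived smokers". Statistical Considerations (analysis of startle potentiation): "Support for the stress neuroadaptation thesis when nicotine deprived would be offered by a Deprivation Status X Threat Uncertainty interaction".

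**The plan's own view of quit context.** C2.4.1, explaining why a single laboratory NRT session was rejected, says that "the affective experience is likely quite different during a temporary deprivation period vs. a similar duration of deprivation" when the latter belongs to a quit meant to be permanent.

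**Text that describes other sessions.** C2.4.1 locates the early-deprivation measurement in a deprived session before quitting. The Statistical Considerations take the deprivation test from two sessions before quitting, treat deprivation as a within-subject factor and label the test Aim 1.2. Their Aim 1.1 is a Smoking Group by Threat Uncertainty interaction. C2.3 itself promises within-subject tests of deprivation.

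**The concern.** Aim 1 is meant to confirm stress neuroadaptation through a selective rise in startle potentiation under uncertain threat when smokers are deprived of nicotine. In the schedule of C2.3 and C3, the deprived group differs from its comparator in two ways at once: it has gone 24 hours without nicotine, and it has begun a real quit attempt. If starting to quit by itself raises the response to uncertain threat, the planned test would report that rise as a deprivation effect. No section names this as a limit on Aim 1. The same startle measures feed Aims 2 to 4, so a misattribution at Aim 1 would carry into how those results are read.

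**Working it through.** **1. The plan's own figure (background only).** C4.3 gives N = 142 for 90% power at a squared multiple partial correlation of 0.10. The significance level is not stated; 5% is assumed here. The figure is recovered if 0.10 is read as f² with 3 numerator df: λ = 14.17, and 14.17/0.10 = 141.7, i.e. 142. The exact noncentral F gives 146. Read literally (f² = 0.10/0.90 = 0.111, 1 df), N is 97 to 99. So 142 is conservative, and nothing below depends on it.

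**2. Cells that the schedule produces.**

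| Session | Group | Nicotine state | Quit attempt begun? |
|---|---|---|---|
| 1 | Non-deprived | usual smoking | no |
| 1 | Deprived | 24 h abstinent, CO below 6 ppm, no study medication yet | yes |
| 2 (2 weeks post-quit) | Active NRT | replacement | yes |
| 2 (2 weeks post-quit) | Placebo NRT | no replacement | yes |

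There is no cell of deprived people who have not begun to quit. At session 1 there is none of people who have begun to quit and are not deprived.

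**3. What session 1 can estimate.** Let Y be uncertain-minus-certain potentiation, D = 1 if deprived, and Q = 1 if the quit attempt has begun. Write E(Y) = μ + δD + κQ. For every participant D = Q, so the group difference is δ + κ. The two columns are identical. Neither covariates nor a larger sample can split the sum.

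**4. Whether other planned data separate δ from κ.**
- *Change from session 1 to session 2.* In the non-deprived group it also crosses the quit date. It further adds medication, task repetition and two weeks of time.
- *Withdrawal and urge scores as covariates.* They are measured after randomization and can be affected by both causes.
- *Active versus placebo at session 2.* Q = 1 for everyone and nicotine is randomized, so this bears on the question, but only indirectly (see the objection).

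**5. Illustration of size.** Assume δ = 0, 150 per deprivation group, and a two-sided 5% t test with df = 298. The noncentrality is d × √(150 × 150/300) = d × √75 = 8.66d.

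| Assumed κ (d) | Noncentrality | Declared significant |
|---|---|---|
| 0.1 | 0.87 | 13.9% |
| 0.2 | 1.73 | 40.8% |
| 0.3 | 2.60 | 73.6% |

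On the partial R² scale with a 1-df F test, values of 0.01, 0.02 and 0.05 give 41%, 69% and 98% at N = 300, and 23%, 41% and 80% at N = 150. For scale, a squared partial correlation of 0.10 with two equal groups corresponds to d = 2√(0.10/0.90) = 0.67.

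**The case against.** The strongest reply has five parts.

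- **Deprivation is randomized, and testing it in a real quit was a reasoned choice.** This stands. A reader might infer that the contrast is invalid. It is not: it validly estimates the effect of the package. One caveat is that C2.3 discontinues only deprived participants who twice fail to abstain. The plan expects fewer than 5% to fail even at the first scheduled session, so this selection should be small.
- **Both groups intend to quit.** This stands. Everyone is motivated to quit, is counseled at screening and sets a quit date. What differs is having started, not commitment. A reader might also infer that the groups differ materially in calendar time and diary exposure, but the documents do not say how long before quitting the non-deprived session falls.
- **The 2-week visit varies nicotine while everyone is past the quit date.** This stands in part. A reader might infer that no data in the trial bear on nicotine versus quitting, and that goes too far. The active-versus-placebo contrast does bear on it. However, it belongs to Aim 4.1, comes later than day 1, replaces nicotine only partially and keeps participants who lapse. It cannot identify δ at session 1.
- **General quit-day stress cancels in the difference score.** This stands. Only a quit-onset effect specific to uncertain threat biases the interaction. The documents give neither its size nor its direction.
- **The Statistical Considerations assume two sessions before quitting, where the overlap would not arise.** That is true of that text, but the schedule in C2.3 and C3 has no such sessions. Inconsistent text does not rescue the interpretation.

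**Conclusion.** The point holds for session 1. Deprivation and having begun to quit overlap completely there, and the plan credits the result to nicotine deprivation and stress neuroadaptation, which is more than this schedule can show. A significant Deprivation Status by Threat Uncertainty interaction would support an effect of deprivation in the context of starting to quit.

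The overlap follows from the schedule in C2.3 and C3 and needs no numerical assumption. The 14%, 41% and 74% are illustrations. They assume no deprivation effect, a quit-onset effect of d = 0.1 to 0.3 specific to uncertain-minus-certain potentiation, and 150 per deprivation group. The documents give none of these; C4.3 states 150 per treatment group, and no deprivation ratio is given. The rates are not evidence that a quit-onset effect exists.

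**What to change.** 1. In Specific Aim 1.1, and in the deprivation contrast of the Statistical Considerations (labeled Aim 1.2 there), restate the test as a between-subject session-1 comparison. It compares CO-verified abstinence at the start of a quit attempt, before study medication, with pre-quit usual smoking, crossed with Threat Uncertainty. Align the aim numbering.
2. State that a significant interaction supports an effect of deprivation in the context of starting to quit, not of nicotine deprivation alone. Cite the randomized active-versus-placebo contrast at 2 weeks as indirect evidence only.
3. Reconcile three places with the schedule in C2.3 and C3: the within-subject wording in C2.3, the deprived session before quitting in C2.4.1, and the two pre-quit sessions with a within-subject deprivation factor in the Statistical Considerations.
4. Report the day of session 1 relative to the quit date by group, including rescheduled sessions.

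The cost is protocol and analysis wording plus one descriptive summary. No participants, visits or treatments change. The downside is a narrower Aim 1 claim.
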